Once AML patients achieve morphologic complete remission with incomplete blood count recovery (CRi) or MDS patients achieve a marrow complete response (Marrow CR) as defined in Section 9.0, decitabine administration may be decreased to 20 mg/m²/day for ten consecutive days every 6 weeks, to limit myelosuppressive toxicity and improve count recovery. After 2 cycles at 6 week intervals, the dose may be reduce to 20 mg/m²/day for five consecutive days in 6 week cycles, at the discretion of the treating physician. After two cycles of five consecutive days of treatment, if the patient meets the definition of CR with complete cytogenetic response as defined in Section 9.0, administration may further be decreased to three consecutive days per cycle at the discretion of the treating physician.

Sample collection for correlative studies:

Bone marrow biopsies should be performed at baseline, at Cycle 1 Day 10 ± 1, and at Day 28 ± 4 of Cycles 1, 2, 4, and 6. Following Cycle 6, bone marrow biopsies should be performed at the discretion of the treating physician to assess for relapse or progression.

Genomic Predictors of Decitabine Response in AML/MDS

Table of Contents

Section	Page
1.0 INTRODUCTION.....	7
1.1 Rationale.....	7
1.2 Decitabine and Hypomethylating agents in AML/MDS.....	9
1.2.1 Pharmacokinetics and Metabolism of Decitabine.....	11
1.2.2 Experience with extended dosing schedules.....	12
1.3 Correlative Studies.....	13
2.0 OBJECTIVES.....	15
2.1 Primary Objective.....	15
2.2 Secondary Objectives.....	15
3.0 PATIENT SELECTION.....	16
3.1 Inclusion Criteria.....	16
3.2 Exclusion Criteria.....	16
3.3 Inclusion of Women and Minorities.....	17
4.0 REGISTRATION PROCEDURES.....	18
4.1 Confirmation of Patient Eligibility.....	18
4.2 Patient Registration in the Siteman Cancer Center OnCore Database.....	18
4.3 Assignment of UPN.....	18
5.0 INVESTIGATIONAL PLAN.....	20
5.1 Summary of Study Design.....	20
5.2 Study Procedures.....	21
5.2.1 Pre-study Procedures.....	21
5.2.2 Baseline Evaluation.....	21
5.2.3 Day 1 of Each Cycle.....	21
5.2.4 Cycle 1 Days 1-10.....	21
5.2.5 Cycle 1 Day 10 ± 1.....	22
5.2.6 Weekly.....	22
5.2.7 Every Other Week.....	22
5.2.8 Cycles 1, 2, 4 and 6 Day 28 ± 4 days.....	22
5.2.9 End-of-Study Procedures.....	22
5.2.10 Post-study Follow-up.....	23
5.3 Duration of Therapy.....	23

5.4	Concomitant Therapy and Supportive Care Guidelines	23
5.4.1	Chemotherapy	23
5.4.2	Growth Factors	24
5.4.3	Transfusions	24

1.0 INTRODUCTION

[figure not shown]
1.1 Rationale

[figure not shown]
Personalized therapy for cancer requires that 1) patient-specific factors (e.g. patient-specific mutations, expression profiles, or pharmacogenomics) influence treatment algorithms, and 2) once therapy is initiated, *in vivo* responsiveness is used to guide further therapy. The modern era of genomics has provided significant insights into cancer pathogenesis by describing patterns of germline and somatic variants, as well as defining disease-specific patterns of gene expression. However, the application and integration of this data with therapeutics remains a difficult task.

AML and MDS are two closely related hematological disorders characterized by ineffective hematopoiesis and malignant expansion of clonal myeloid cells. Both AML and MDS frequently occur in elderly patients and some cases are secondary and/or related to long-term bone marrow damage after radiation or chemotherapy. Current therapy for AML consists of cytotoxic chemotherapy followed by consolidation chemotherapy or stem cell transplantation. Using these approaches, current cure rates may be as high as 60% for patients younger than 60 with good risk cytogenetics (e.g. t(15;17), t(8;21), inv(16)).[4] Outcomes in patients ≥ 60 years old and with relapsed disease remain poor with 2 year survival of only ~25%.[5] Historically, the available treatment for MDS has been symptomatic and has not been shown to be effective in producing sustained improvement in hematopoiesis or in delaying leukemic evolution[6, 7].

Current AML therapy is poorly tolerated in elderly and pre-treated patients due to hematologic and non-hematologic toxicities; following such therapy, patients typically require 3-4 weeks of hospitalization for treatment of neutropenic fevers and for regular transfusions. Even among the relatively healthy patients enrolled in clinical trials, induction mortality in the elderly can be as high as 20-40% following standard induction therapy,[8-11] and moderate to severe non-hematologic toxicity occurs in at least an additional 30% of patients.[9, 12-14] Consequently, many older AML patients are not offered traditional intensive chemotherapy, but receive supportive care alone.[15] More effective and less toxic therapies are needed to provide durable remissions in a significant proportion of elderly AML in populations.

We and others have recently used whole genome sequencing to identify recurrent, somatic mutations in AML and MDS patients in four genes that are involved in methylcytosine regulation: *DNMT3A*, *IDH1*, *IDH2*, and *TET2*. [29-37] Collectively, nearly half of all AML/MDS patients have a mutation in one of these four genes. *DNMT3A* mutations are associated with an adverse outcome in AML patients treated with cytotoxic chemotherapy. [35, 38] However, it is not yet clear whether the presence of mutations in one or more of these genes is associated with response or resistance to decitabine.

In this study, we will treat patients with the current state-of-the-art decitabine schedule. [3] We will perform exome sequencing on all patients and correlate response with mutation status, rate of mutation clearance, expression profile, plasma decitabine levels, and DNA

methylcytosine content reduction. This approach will comprehensively assess genomic and pharmacologic parameters that could clinically predict patient response to decitabine.

In this study, we will combine analysis of patients with AML and MDS. Recent genomic analysis has shown that AML and MDS have shared mutations in many of the same genes, shared patterns of mutation acquisition, and shared patterns of mutation evolution.[39, 40] Furthermore, MDS, like AML, presents with clonal hematopoiesis, even when the morphologic blast count is zero.[36] Because this study will identify and track the rate of clearance of patient specific mutations, and because decitabine has been shown to have efficacy in both AML and MDS patients, [2, 3, 16-19, 41-45] combining analysis of AML and MDS patients is reasonable. Asymptomatic MDS patients are excluded because these patients are typically followed with watchful-waiting rather than with chemotherapy.

1.2 Decitabine and Hypomethylating agents in AML/MDS

[Redacted]

[Redacted]

[Redacted]

[Redacted]

[Redacted]

[Redacted]

[Redacted]

[Redacted text block]

[figure not shown]
[Redacted]	[Redacted]	[Redacted]
[Redacted]	[Redacted]	[Redacted]
[Redacted]	[Redacted]	[Redacted]
[Redacted]	[Redacted]	[Redacted]
[Redacted]	[Redacted]	[Redacted]
[Redacted]	[Redacted]	[Redacted]
[Redacted]	[Redacted]	[Redacted]
[Redacted]	[Redacted]	[Redacted]
[Redacted]	[Redacted]	[Redacted]
[Redacted]	[Redacted]	[Redacted]

[Redacted text block]

[Redacted text block]

1.2.2 Experience with extended dosing schedules

[Redacted text block]

1.3 Correlative Studies

All correlative studies will be collected under HRPO# 201011766 (“Tissue Acquisition for Analysis of Genetic Progression Factors in Hematologic Diseases”) that all patients will be concurrently enrolled in. The goals of the correlative studies include:

1. To correlate patient-specific mutations with response to decitabine.
We will perform exome sequencing of each patient’s pre-study bone marrow sample and skin sample. We will determine AML/MDS-associated variants found in the bone marrow, but not skin sample. We will correlate the presence of mutations with response (especially mutations in *DNMT3A*, *IDH1*, *IDH2*, and *TET2*). This study is powered to identify mutations with >80% sensitivity to predict decitabine response if used as a clinical assay.
2. To correlate the velocity and depth of response with response to decitabine.
We will assess tumor burden by allele frequency of patient-specific mutations in bone marrow samples collected pre study, Cycle 1 Day 10±1, Cycle 1 Day 28±4, and Cycle 2 Day 28±4. We will assess mutations in at least 24 recurrently mutated genes (including, but not limited to: *FLT3*, *DNMT3A*, *NPM1*, *TET2*, *WT1*, *IDH1*, *IDH2*, *RUNX1*, *NRAS*, *TP53*, *U2AF1*, *KRAS*, *PHF6*, *MSTP9*, *PTPN11*, *KIT*, *SMC3*, *PRUNE2*, *ETV6*, *CEBPA*, *SMC1A*, *ASXL1*, *STAG2*, *RAD21*) as well as all patient-specific mutations discovered during exome sequencing. The leukemic allele frequency will be measured using the Illumina MySeq or HiSeq platform using DNA capture by gene specific biotinylated-oligonucleotides. Patient bone marrow samples will be assessed pre-study, Cycle 1 Day 10 ± 1, Cycle 1 Day 28 ± 4, and Cycle 2 Day 28 ± 4 and compared with patient specific skin samples (normal control). The velocity of response will be calculated as the natural log rate of patient-specific mutation allele frequency clearance. Depth of response will be defined as the lowest patient-specific mutation

allele frequency in a bone marrow sample. The velocity and depth of tumor response will be correlated to:

- Achievement of clinical CR,
- Time to best response,
- Mutational status,
- Time to disease progression.

Because all patient-specific exome-discovered mutations will be assessed a second time in the primary bone marrow sample as well as the Cycle 1 Day 10 \pm 1, Cycle 1 Day 28 \pm 4, and Cycle 2 Day 28 \pm 4 bone marrow samples, this study will also serve to validate all exome-discovered mutations. This is important, because exome sequencing is associated with a 20-50% false-discovery rate depending on type I error tolerated (mutation-calling algorithms are typically set for greater sensitivity than specificity). Thus, many mutations discovered during exome sequencing are incorrect. This second analysis of these mutations will serve to exclude these false positive calls.

3. To correlate the bone marrow expression profile from pre-study and Cycle 1 Day 10 \pm 1 with response to decitabine.

We will correlate expression signatures, and changes in expression signatures, with:

- Achievement of clinical CR,
- Mutation status.

4. To correlate the extent of bone marrow DNA hypomethylation on Cycle 1 Day 10 \pm 1 with response to decitabine.

We will assess the percent reduction in bone marrow methylcytosine content using LC-MS. Patients will be evaluated pre-study and Cycle 1 Day 10 \pm 1. The change in DNA methylcytosine content will be correlated to:

- Achievement of clinical CR,
- Change in expression signature.

This will determine whether inadequate blast exposure to decitabine correlates with drug resistance.

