A power analysis was performed using Chi-square test for the association between mutation and response to decitabine. The frequency of *DNMT3A*, *IDH1/2*, and *TET2* mutations in AML and MDS patients are each between 15% and 30% in multiple cohorts.[29-37] **Table 3** shows the minimal detectable differences of response rates between mutant and wild-type cases, assuming an expected overall 45% CR/CRi rate and 80% power. For an average of 20% frequency of a mutated gene, for example, 100 patients will provide 80% power to detect 30% difference at a 2-sided 0.1 alpha error. The purpose of this study is to determine whether any of these mutations result in a clinically significant association that would warrant pre-treatment testing. We believe that a reasonable cut off would be if at least 30% of clinical response could be attributed to the presence of a specific mutation. However, we anticipate that more power could be achieved as we assess patient groups with combined characteristics (e.g. *DNMT3A* mutation or loss of *DNMT3A* expression). In addition, we expect that the majority of the enrolled 125

Table 3. Detectable mutation associated response rates (80% power, $\alpha = 0.05$)

Total N	% of patients with a given mutation	Detectable response difference	Sensitivity of mutation to predict response at minimum detectable response difference*
100	15%	0.40	80%
	20%	0.35	75%
	30%	0.30	67%
	40%	0.27	61%
	50%	0.26	58%

* Assuming the overall response rate (CR/CRi) of 45%

patients can be used in the analysis (since all of our molecular information will be acquired within 30 days of enrollment, we anticipate a drop-out rate of 20% or less).

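### Table 3's sensitivity column is the response rate in mutation carriers (PPV), and the sensitivity above 80% stated in Section 1.3 cannot hold for any single named gene

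*Combined protocol and SAP*

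**What the plan says.** Section 1.3, under the first correlative goal, says: "This study is powered to identify mutations with >80% sensitivity to predict decitabine response if used as a clinical assay". It gives no definition of sensitivity and no calculation.

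The supporting figures are in Section 14.2.2. Its text says that Table 3 "shows the minimal detectable differences of response rates between mutant and wild-type cases", "assuming an expected overall 45% CR/CRi rate and 80% power", with 100 patients. For mutation frequencies of 15, 20, 30, 40 and 50%, the table gives detectable differences of 0.40, 0.35, 0.30, 0.27 and 0.26. A last column, headed "Sensitivity of mutation to predict response at minimum detectable response difference", gives 80, 75, 67, 61 and 58%.

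On how common the mutations are, Section 14.2.2 says of DNMT3A, IDH1/2 and TET2 that "mutations in AML and MDS patients are each between 15% and 30% in multiple cohorts". Section 1.1 adds: "Collectively, nearly half of all AML/MDS patients have a mutation in one of these four genes". The Section 1.3 sentence and Table 3 appear with the same content in each protocol version in the combined document.

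**The concern.** Sensitivity of a mutation for response is the proportion of responders who carry it. A mutation found in a small minority of patients cannot be present in most responders when 45% of patients respond. Yet the table gives its highest sensitivity, 80%, to the rarest mutation.

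The stated purpose in Section 14.2.2 is to judge whether a mutation merits testing before treatment. Sensitivity and PPV answer different questions there. At 20% frequency and the tabulated difference, 73% of carriers respond, but about 68% of responders do not carry the mutation, and wild-type patients still respond at 38%. A reader who takes the printed 75% as sensitivity would conclude that a negative test identifies mostly non-responders and misses few responders. The design's own figures say otherwise.

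**Working it through.** **Inputs, all from the plan.** Overall response R = 0.45 and N = 100 (Section 14.2.2 and Table 3). Mutation frequency f and difference d, mutant minus wild-type, are taken as printed in Table 3. Single-gene frequency is 0.15 to 0.30 (Section 14.2.2).

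**Formulas.** With R fixed:
- response rate in carriers, p1 = R + (1 − f)d. This is P(response | mutation), the PPV.
- response rate in wild-type, p0 = R − f·d.
- sensitivity = P(mutation | response) = f·p1/R.
- ceiling on sensitivity, reached if every carrier responds = f/R (at most 1).

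**Example, f = 0.20, d = 0.35.** p1 = 0.45 + 0.80 × 0.35 = 0.73. p0 = 0.45 − 0.20 × 0.35 = 0.38. Sensitivity = 0.20 × 0.73/0.45 = 0.324. Ceiling = 0.20/0.45 = 0.444.

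| f | d | Printed column | p1 (PPV) | p0 | True sensitivity | Ceiling |
|---|---|---|---|---|---|---|
| 15% | 0.40 | 80% | 79.0% | 39.0% | 26.3% | 33.3% |
| 20% | 0.35 | 75% | 73.0% | 38.0% | 32.4% | 44.4% |
| 30% | 0.30 | 67% | 66.0% | 36.0% | 44.0% | 66.7% |
| 40% | 0.27 | 61% | 61.2% | 34.2% | 54.4% | 88.9% |
| 50% | 0.26 | 58% | 58.0% | 32.0% | 64.4% | 100% |

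The printed column reproduces as PPV to within 2 points in every row. It does not reproduce as sensitivity in any row. The two also move in opposite directions: the printed column falls as f rises, as PPV does, while sensitivity rises. Rounding cannot explain that.

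**Other readings tried.** None of these gives the printed column:
- specificity: 94, 90, 81, 72, 62%
- NPV: 61, 62, 64, 66, 68%
- overall accuracy: 63 to 65%
- 45% taken as the wild-type rate: PPV 85, 80, 75, 72, 71% and sensitivity 25, 31, 42, 52, 61%
- direction reversed, so that wild-type status predicts response: sensitivity 96, 92, 84, 74, 64%

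**Check by counts.** 100 patients at 45% give 45 responders. In the 15% row there are 15 carriers, and 80% sensitivity would need 0.80 × 45 = 36 carriers among the responders. In the 20% row, 75% would need about 34 out of 20 carriers. In the 30% row, 67% would need all 30 carriers to respond, leaving 15 responders among 70 wild-type patients (21%), a difference of 0.79 against the tabulated 0.30.

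**Frequency needed for 80%.** f must be at least 0.80 × 0.45 = 0.36. At f = 0.50, 80% sensitivity needs p1 = 0.80 × 0.45/0.50 = 0.72 and p0 = (0.45 − 0.36)/0.50 = 0.18, a difference of 0.54 against the tabulated 0.26.

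**The case against.** The sentence in 1.3 speaks of mutations in general, and the four genes are only singled out for emphasis. The plan examines at least 24 genes and all variants found by exome sequencing. It also expects combinations: the four genes together reach nearly half of patients, that composite is a planned subgroup in Section 14.2.5, and 14.2.2 mentions combined characteristics. Section 3.1, in the versions requiring adverse-risk disease, lists TP53 mutation as one route to eligibility. Its frequency in the enrolled patients is not given and might exceed 36%. For a composite at 50%, a difference of 0.54 would be detected with more than 99% power at N = 100 and two-sided alpha 0.05. All of this stands. A reader might infer that the design rules out 80% sensitivity altogether, but the documents do not support that. The limit applies to each named gene taken alone.

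A reader might also infer an error in the nearby statement that "a reasonable cut off would be if at least 30% of clinical response could be attributed to the presence of a specific mutation". That does not follow, because the plan does not define attribution. Shortly before, the same paragraph refers to a 30% difference in response rates, and on that reading the wording is merely loose. Read as the share attributable among carriers, (p1 − p0)/p1, Table 3 gives 51, 48 and 45% at f = 15, 20 and 30%, all above 30%. Even as a share of all responses, a gene at 30% would need a carrier response rate of 76.5%, which is attainable.

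Finally, sensitivity enters neither the test, alpha, power nor sample size, and no planned analysis reports it. The planned contingency tables would allow it to be calculated correctly. That limits the consequence but does not make the label or the sentence right.

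**Conclusion.** The column is mislabelled: it is the response rate in carriers. At Table 3's differences, true sensitivity is 26 to 44% for the named genes singly (f = 15 to 30%) and 26 to 64% across all rows. With ceilings of 33, 44 and 67% at f = 15, 20 and 30%, the statement in 1.3 cannot hold for any one of them. It could hold only for a mutation or composite with f of at least 36%. Even at f = 50% that takes about twice the tabulated difference, and the tabulated difference itself gives 64%.

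The result rests on R = 45% and the plan's frequency range. A gene at 30% could reach 80% only if R were 37.5% or lower and every carrier responded. Counting partial remissions as response, as Section 14.2.3 does for overall response, could only raise R or leave it unchanged. At an assumed R of 55% the ceilings at f = 15 to 30% would be 27 to 55%.

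**What to change.** In Section 1.3, delete the sentence on sensitivity, or replace it with the carrier response rate (PPV) that the design can detect: about 79% at f = 15%, 73% at 20% and 66% at 30%, given 45% overall response.

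In Table 3, relabel the last column as response rate in mutation carriers (PPV), and add a column of true sensitivity: 26, 32, 44, 54 and 64%.

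The cost is wording only. The stated assay performance becomes less favourable. The test and sample size stay as they are.

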3.0 PATIENT SELECTION

3.1 Inclusion Criteria

All of the following:

- Patient must have non-M3 AML or MDS
- An adverse risk karyotype defined by:
 - Complex karyotype by cytogenetics, or
 - Deletion of all or part of chromosome 5, 7, 12, or 17 defined by FISH or cytogenetics, or
 - Somatic TP53 mutation

All of the following:

1. Patient must have an ECOG performance status ≤ 2 .
2. Patient must have $>10\%$ disease burden measured by cytomorphology, flow cytometry, or cytogenetics.
3. Patient must have peripheral white blood cell count $\leq 50,000/\text{mcl}$.
4. Patient must have adequate organ function, defined as:
 - a. Total bilirubin $\leq 1.5 \times \text{ULN}$
 - b. AST/ALT $\leq 2.5 \times \text{ULN}$
 - c. Serum creatinine $\leq 2.0 \times \text{ULN}$
5. Patient must have undergone ≤ 2 cycles of prior hypomethylating agent (decitabine or azacitidine).
6. Patient must be enrolled in HRPO# 201011766 (“Tissue Acquisition for Analysis of Genetic Progression Factors in Hematologic Diseases”).
7. Patient must be ≥ 18 years of age.
8. Patient must be able to understand and willing to sign an IRB-approved written informed consent document.

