14.2.3 Secondary Endpoint Analyses

The overall response rate (CR/CRi/PR) and complete response rate (CR/CRi) will be compared with historical controls[2], and the 95% confidence intervals will be provided.

The rate of patient specific mutation clearance after 10, 28, and 56 days of therapy will be determined using an Illumina based platform. We will compare the rate of mutation clearance between the patients who achieve a CR/CRi after 4 cycles and those who do not. We anticipate that we will identify between 6 and 25 exonic SNVs per case (the range obtained with >200 AML samples sequenced to date with whole genome or exome sequencing), and that the expected 95% confidence interval of the mean variant allele frequency will be $\pm 2.56\%$ and $\pm 1.25\%$,

respectively, if we assume an anticipated standard deviation of 3.2% within the same clone. The change of tumor burden over time and its association with clinical response will be assessed using 2-way ANOVA for repeated measurement data, followed by the ad-hoc multiple comparisons for between-group differences (e.g., responders vs. non-responders) at given time points as well as the between-time differences within each group. The resultant critical P values will also be corrected using permutation analysis for multiple testing.

The percent decrease in bone marrow methylcytosine will be calculated on day 10 ± 1 . We will compare this reduction with previously published data and between the patients who achieve CR/CRi and those who do not. The correlation of peak plasma levels of decitabine with response will be assessed using 2-sample t-test or Mann-Whitney non-parametric rank-sum test as appropriate. The change of total bone marrow DNA methylcytosine from baseline and its association with both steady-state plasma drug levels and response will be assessed using 2-way ANOVA for repeated measurement data, followed by the ad-hoc multiple comparisons for between-group differences (e.g., responders vs. non-responders) and between-time differences. Similar analyses will be performed for the correlation of expression profiles and SNP analysis with pharmacokinetic data.

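### Tumor burden and clearance velocity are taken from raw allele frequency with no copy-number correction, in a population whose entry rule enriches for copy-number loss

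*Combined protocol and SAP*

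**What the plan says.** Section 1.3 item 2 sets the measure: "We will assess tumor burden by allele frequency of patient-specific mutations in bone marrow samples". It then defines speed: "The velocity of response will be calculated as the natural log rate of patient-specific mutation allele frequency clearance". The depth rule begins "Depth of response will be defined as the lowest patient-specific mutation" and refers to allele frequency in a marrow sample. Velocity and depth are to be correlated with clinical CR, time to best response, mutational status and time to progression.

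Section 14.2.3 compares clearance between patients who do and do not reach CR/CRi after 4 cycles. It expects 6 to 25 variants per case and gives 95% intervals of ±2.56% and ±1.25% for the mean VAF, "respectively, if we assume an anticipated standard deviation of 3.2% within the same clone". Its power paragraph uses 4.7% as the largest SD seen.

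Section 3.1, in the apparently current protocol that opens the combined file, requires one of three findings. The first route reads "Complex karyotype by cytogenetics, or"; the second, which concerns chromosome loss, reads "Deletion of all or part of chromosome 5, 7, 12, or 17 defined by FISH or cytogenetics, or"; and the third, at gene level, is "Somatic TP53 mutation". It also asks for more than 10% "disease burden measured by cytomorphology, flow cytometry, or cytogenetics".

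No readable section brings copy number or zygosity into the VAF calculation. The skin sample serves as the normal control. Karyotype and FISH are done on the scheduled marrows but are not linked to VAF. No rule says how several variants become one value per patient.

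**The concern.** Raw VAF is proportional to the fraction of leukemic cells when a variant is heterozygous in a two-copy region. It is not proportional when the clone has lost the other copy: as the clone shrinks, normal cells contribute two normal copies each and the VAF falls faster than the cell fraction. Three of the protocol copies in the combined file (those without the karyotype rule) define entry by age, relapse or symptomatic MDS, and they carry the same velocity and SD text. The measure therefore appears to have been kept unchanged when entry moved to a group enriched for deletions.

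At stake are the secondary and correlative analyses. TP53 is both an entry route and one of the tracked genes, deletion of chromosome 17 is another entry route, and velocity is to be correlated with mutational status. An error in velocity that depends on the deletion could therefore be linked to the variable it is compared against. Mixing the two kinds of variant also undermines the assumption that variants in one clone share a VAF with SD 3.2%.

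**Working it through.** **The plan's own figures.** Half-width = 1.96 × SD/√n. For n = 6: 1.96 × 3.2/√6 = 2.56. For n = 25: 1.96 × 3.2/√25 = 1.25. Both match 14.2.3. A two-sided two-sample t-test gives power of 99.8%, 98.6%, 91.2% and 82.8%, against the stated >99%, >98%, 91% and 82%. The plan's arithmetic is sound under its assumption.

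**VAF and cell fraction.** Let p be the fraction of marrow cells in the clone.
- Heterozygous, two copies: p mutant copies out of 2, so VAF = p/2.
- Other copy deleted in the same cells: p mutant copies out of p + 2(1−p), so VAF = p/(2−p).

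**Velocity.** Log clearance is ln(VAF₀/VAF₁). Dividing the hemizygous by the heterozygous value and subtracting 1 gives

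excess = ln[(2−p₁)/(2−p₀)] / ln(p₀/p₁),

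which is positive whenever p falls.

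Example, p from 0.90 to 0.45: the heterozygous variant goes 0.450 to 0.225 (ln = 0.693) and the hemizygous one 0.818 to 0.290 (ln = 1.036), an excess of 49.5%. From 0.90 to 0.09 the values are 2.303 and 2.854, an excess of 24.0%.

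| Baseline p (assumed) | 50% fall | 90% fall |
|---|---|---|
| 0.11 | 4.1% | 2.2% |
| 0.50 | 22.2% | 11.4% |
| 0.70 | 34.4% | 17.2% |
| 0.90 | 49.5% | 24.0% |
| 1.00 | 58.5% | 27.9% |

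Smaller falls give a larger relative excess (25% fall: 27.8% at 0.50, 64.7% at 0.90). Larger falls give less (99% fall: 12.9% at 0.90).

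**If velocity comes from the mean VAF.** With one hemizygous variant among six and p from 0.90 to 0.45, the mean goes from (5 × 0.450 + 0.818)/6 = 0.511 to (5 × 0.225 + 0.290)/6 = 0.236. The excess is 11.6%, or 5.2% for a 90% fall. At baseline 0.50 it is 4.4% and 2.2%. With one among 25 at 0.90 it is 3.0% and 1.3%.

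**Within-clone SD.** The gap between the two kinds of variant is 8.3 points at p = 0.50, 18.8 at 0.70 and 36.8 at 0.90. With one of six shifted by that gap, SD² = 3.2² + gap²/6:
- p = 0.50: SD 4.7 (4.67), half-width ±3.7
- p = 0.70: SD 8.3, half-width ±6.7
- p = 0.90: SD 15.4, half-width ±12.3

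The planned 3.2% is exceeded in all three cases, and the 4.7% maximum at 0.70 and above.

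**Where the effect is small or absent.** For depth, the ratio of hemizygous to heterozygous VAF is 1.05 at p = 0.10 and 1.005 at p = 0.01. With copy-neutral loss of heterozygosity VAF = p, so the level doubles but the log fall is unchanged.

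**Conversion.** Inverting gives p = 2·VAF (heterozygous, two copies) and p = 2·VAF/(1+VAF) (hemizygous). The hemizygous values 0.818 and 0.290 convert to 0.90 and 0.45, so log clearance is 0.693 and the excess is 0%.

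**The case against.** The strongest reply concerns size. The 24–49% range needs a baseline clonal fraction of about 90%, which the documents do not give. Entry requires only more than 10% burden, where the excess is 2–4%. That stands, although section 1.1 notes that clonal hematopoiesis can be present with no blasts, so clonal fractions well above the blast count are possible.

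The range is also per variant. Section 14.2.3 speaks of a mean VAF over 6 to 25 variants, and averaging dilutes the error. That stands too, but section 1.3 gives no combining rule and its wording permits a per-mutation reading.

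The affected share is unknown. Entry is by any one of three routes, so not every patient has a deletion. The mutated copy must be the one retained, in the same cells as the deletion. Patients enrolled under the protocol copies without the karyotype rule would dilute the effect further.

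A reader might infer that TP53 carriers will be falsely declared faster clearers, at some calculable error rate. The documents do not support that. No such test is specified: mutational status is one of four unranked correlates, and the comparison in 14.2.3 is by CR/CRi. Any error rate would rest on an assumed baseline, an assumed hemizygous share, and one variant standing for the whole patient.

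**Conclusion.** The point holds as a bias of known direction and uncertain size. Applied as written, the velocity rule overstates clearance for a variant on the only retained copy, by about 2–58% for 50–90% falls over baseline fractions of 0.11–1.00. This assumes that mutation and deletion share the same cells.

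It would go too far to read 24–49% as a typical patient-level error. That is a single-variant figure at 0.90, and it becomes about 5–12% when one of six variants is averaged in. Nor does the point reach the primary analysis, which uses the presence of mutations rather than their frequency. Depth is little affected at low residual burden. What remains is an avoidable distortion of a secondary measure, a precision statement that fails where the two kinds of variant are mixed at high burden, and a missing rule for combining variants. The plan should correct these, because doing so is cheap.

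**What to change.** In section 1.3 item 2 and section 14.2.3:
- Compute burden and velocity from heterozygous variants in copy-neutral autosomal regions. Alternatively, convert each VAF to a mutant-cell fraction where local copy number is known: p = 2·VAF, or p = 2·VAF/(1+VAF) if hemizygous.
- State how variants are combined into one value per patient and time point.
- Use that value in the correlations with mutational status and response.
- State that the 3.2% SD and the resulting intervals apply to copy-neutral heterozygous variants.

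The cost is analysis work on karyotype, FISH and exome data already planned; no new samples or visits are needed. Two limits should be acknowledged. The documents describe exome sequencing for finding variants, so its use for local copy number would have to be specified. Karyotype and FISH alone do not show that a mutation and a deletion share the same cells, which favors the copy-neutral restriction where this is unclear. The downside is fewer usable variants in some patients.
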